6.4 ORDERING UMBRALISIB

Once the clinical study site receives regulatory approval (IRB/IEB), and the Sponsor and/or Sponsor designee performs the Site Initiation Visit and inspection of pharmacy, and determines the site to be officially open for enrollment, and once a subject is identified, a shipment of pre-determined quantity of umbralisib will be shipped to the clinical study site.

Upon receipt of treatment supplies, the Pharmacist or authorized designee should update the accountability forms for umbralisib. If any abnormality on the supplied bottles (umbralisib) is observed, the Pharmacist or authorized designee must document that on the acknowledgement of receipt and contact that Sponsor and/or Sponsor designee.

6.5 DURATION OF THERAPY

In the absence of treatment delays due to adverse event(s), treatment should continue through Cycle 1 and beyond unless one of the following criteria applies:

- Disease progression or inter-current illness that prevents further treatment.
- Patient decides to withdraw from the study, or changes in the subject's condition render the subject unacceptable for further treatment in the judgment of the investigator.

^{**}Supportive Care – Aggressive management of lipid, glucose, other metabolic disorders, viral infections, etc. Important: Before initiating steroids, check for viral hepatitis or CMV infection.

Study drug will be made available to responding subjects for a total of three years from
initiation of therapy. If umbralisib becomes commercially available during the active period
on study, an attempt will be made to obtain this agent through commercial insurance. If
coverage is not available, it will be provided for a period of three years as stated above.

During the study period, subjects will be evaluated for response by CT and/or MRI during Cycles 3, 6, 9, 12 and then at least every 6 cycles for 24 cycles then every 12 cycles thereafter (+/- 14 day window). Subjects should remain on study treatment until the occurrence of definitive disease progression, unacceptable toxicity, or withdrawal from the study due to investigator decision or other reasons. Subjects who discontinue from study treatment and have not progressed should continue to be followed for progression, if agreeable, approximately every 3 months. If the subject discontinues after cycle 12 for reasons other than disease progression, they should continue to be followed for progression approximately every 6 months for 24 cycles then every 12 cycles thereafter (+/- 14 day window).

7 STUDY MEDICATION OVERVIEW AND SAFETY

7.1 UMBRALISIB

Chemical Name: Umbralisib tosylate

Other Names: TGR-1202

Classification: Phosphatidylinositol-3-Kinase (PI3K) Delta Inhibitor

Formulation: See Investigator Brochure

Mode of Action: Irreversibly inhibits activity of the Class I Delta isoform of PI3K

How Supplied: 200 mg tablets

Storage: Store at 25°C. Excursions permitted 15°C to 30°C.

Stability: Retest dates will be provided periodically by Sponsor.

Route of

Administration: Oral

Packaging: Umbralisib is provided in HDPE bottles each containing 30 tablets and a silica

gel canister as a desiccant.

Availability: Umbralisib is available from TG Therapeutics.

7.1.1 COMPREHENSIVE ADVERSE EVENTS AND POTENTIAL RISKS LISTS (CAEPRS)

The following adverse events were observed in subjects treated with single agent umbralisib and were considered at least possibly related to the study medication. The preliminary safety data as of May 1, 2018 is provided for a total of 136 subjects exposed to single agent umbralisib with a maximum follow up of 5+ years. See the latest umbralisib Investigator's Brochure for updated safety information.

VERY COMMON (≥10%)

Blood and Lymphatic System Disorders: neutropenia

Gastrointestinal Disorders: nausea, diarrhoea, vomiting

General Disorders and Administration Site Conditions: fatigue

7.1.1.1 COMMON (≥ 2% - < 10%)

Blood and Lymphatic System Disorders: anaemia, thrombocytopenia, leukocytosis, lymphocytosis

Ear and Labyrinth Disorders: tinnitus

Eye Disorders: vision blurred

TGR-1202-201-CLL

Gastrointestinal Disorders: constipation, abdominal pain, abdominal distension, dyspepsia, colitis, dry mouth

General Disorders and Administration Site Conditions: pyrexia, oedema peripheral

Infections and Infestations: pneumonia, oral candidiasis

Injury, Poisoning and Procedural Complications: contusion

Investigations: weight decreased, alanine aminotransferase increased, aspartate aminotransferase increased, blood creatinine increased

Metabolism and Nutrition Disorders: decreased appetite, dehydration, hyperglycaemia, hypokalaemia, hypophosphataemia

Musculoskeletal and Connective Tissue Disorders: muscle spasms, pain in extremity

Nervous System Disorders: dizziness, headache, dysgeusia, tremor

Psychiatric Disorders: insomnia

Respiratory, Thoracic and Mediastinal Disorders: cough

Skin and Subcutaneous Tissue Disorders: rash maculo-papular, alopecia, night sweats, pruritus, rash

8 MEASUREMENT OF EFFECT

During the study period, all subjects will be evaluated for response by CT and/or MRI during Cycles 3, 6, 9, 12 and then at least every 6 cycles for 24 cycles, then every 12 cycles thereafter or more frequent if warranted. All efficacy assessments have a +/- 14- day window. The determination of response and progression will be based on IWCLL criteria (Hallek M, 2008).

CT scan is the preferred method of tumor assessment but MRI may be used at the investigator's discretion. The same method of assessment and the same technique should be used to characterize each identified and reported lesion at baseline and throughout the study. All baseline assessments to characterize disease will be performed within 30 days of Cycle 1 Day 1, prior to initiation of therapy.

Subjects should remain on study treatment until the occurrence of definitive disease progression, unacceptable toxicity, or withdrawal from the study due to investigator decision or other reasons. Subjects who discontinue from study treatment (either for toxicity or physician choice) and have not progressed will continue to be followed for progression as per the protocol.

8.1 METHOD OF ASSESSMENT

In addition to clinical examination, radiographic evaluation will be used in all subjects enrolled. CT scan is the preferred method for radiographic tumor assessment. MRI scanning may be used at the investigator's discretion in subjects for whom this may be a preferred alternative to CT scanning; however, if MRI is performed, a non-contrast CT of the chest should be performed. Contrast-enhanced scanning is preferred, but iodine-containing or gadolinium contrast material may be omitted in subjects for whom use of a contrast agent would be medically contraindicated. Chest x-ray, ultrasound, endoscopy, laparoscopy, PET, radionuclide scans, or tumor markers will not be considered for response assessment. If IV contrast is not used at baseline, then it should not be used with subsequent response assessments to maintain consistency.

For radiographic evaluations, the same method of assessment and the same technique (e.g., scan type, subject position, dose of contrast, injection/scan interval) should be used to characterize each identified and reported lesion at baseline and during study treatment and follow-up. However, if a subject is imaged without contrast at baseline, subsequent assessments should not be performed with contrast, unless medically contraindicated.

All relevant clinical and radiographic information required to make each tumor status assessment must be made available for source verification.

8.2 RESPONSE REVIEW

The review of radiographic and clinical data by the study investigators will be performed on an ongoing basis. De-identified images should be available if the Sponsor requests to confirm any objective response observed.

8.3.1 TARGET LESIONS

At baseline, up to 6 lymph nodes should be selected as target lesions (if measurable disease is present) that will be used to quantitate the status of the disease during study treatment. Ideally, the target lesions should be located in disparate regions of the body. Only peripheral nodes need be selected as target lesions. However, it is optimal if mediastinal and retroperitoneal areas of disease are assessed whenever these sites are involved.

Target lesions should be measured and recorded at baseline and as per the study assessment schedule. The cross-sectional dimensions (the largest cross-sectional diameter, i.e., the LD × LPD) will be recorded (in cm) for each target lesion. The product of the perpendicular diameters (PPD) (in cm²) for each target lesion and the sum of the products (SPD) (in cm²) for all target lesions will be calculated and recorded. The baseline SPD will be used as references by which objective tumor response will be characterized during treatment. The nadir LD of individual lesions and the nadir SPD will be used as references by which CLL progression will be characterized. All LD and LPD diameters will be reported in centimeters and all PPDs and SPDs will be reported in centimeters squared.

A nodal mass may be selected as a measurable nodal target lesion if it is > 1.5 cm in long axis diameter and > 1.0 cm in short axis diameter.

A new node that measures >1.5 cm in the LD and >1.0 cm in the LPD will be considered progressive disease.

In cases in which a large lymph node mass has split into multiple components, all subcomponents regardless of size will be used in calculating the SPD. Progression of the lesion will be based on the SPD of sub-components. Lesion sub-components will have the true PPDs calculated. Similarly, lesion sub-components that are visible but neither abnormal nor measurable will have the default PPD of $1.0~\rm cm^2$ ($1.0~\rm cm \times 1.0~\rm cm$) used in calculating the SPD.

If lesions merge, a boundary between the lesions will be established so the LD of each individual lesion can continue to be measured. If the lesions have merged in a way that they can no longer be separated by this boundary, the newly merged lesion will be measured bi-dimensionally.

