5 STUDY ASSESSMENTS AND TREATMENT SCHEDULE

Error! Reference source not found. The Table below lists study assessments that should be performed at each study visit.

STUDY ASSESSMENTS AND TREATMENT SCHEDULE

All cycles are 28 days	Screening	Cycle 1 ¹		Cycles 2 - 6 ²	> Cycle 6 ³	ЕОТ	30 day	
	D-30 to D0	D1	D8	D15	D1	Every 3 cycles	EOI	F/U
Informed Consent	X							
Medical History	X							
ECOG Performance Status	X	X			X	X	X	
Physical Examination/Vitals (Weight, Temp, BP, HR, RR)	X	X	X	X	X	x	X	
EKG (QtcF)	X							
Serology HCV, HBV, CMV	X4							
CMV surveillance					C3&6	X5		
Hematology	X	X	X	X	X	X	X	
Chemistry	X	X	X	X	X	X	X	
CT Imaging (neck, chest, abdomen, pelvis)	X ⁶	During Cycles 3, 6, 9, 12 and at least every 6 cycles for 24 cycles, then every 12 cycles thereafter or more frequent if warranted (+/- 14 days)			X ⁷			
Serum Pregnancy Test	X8		1					
Urine Pregnancy Test ⁹					X	X		
Collect Buccal Swab for Somatic DNA ¹⁰	Х							
Correlative Labs (PB) ¹⁰	Х				Cycle 2		Disease progression	
Peripheral Blood ¹¹	X							
Umbralisib	Daily Days 1 - 28							
Bone Marrow Biopsy ¹²	X							
AE Assessment		X	X	X	X	X	X	X13
Con med Assessment		X	X	X	X	X	X	

¹ Physical Exam, Vitals, ECOG, treatment administration, AEs, conmeds, hematology, serum chemistry visit days have +/- 1 day window. Assessments must be done within the specified window, but only prior to initiation of next cycle.

² Physical Exam, Vital Signs, ECOG PS, treatment administration, AEs, conmeds, hematology, serum chemistry visit days have +/- 3 day window in Cycles 2 - 6. Assessments must be done prior to treatment administration. Assessments must be done within the specified window, but only prior to initiation of next cycle.

³ Physical Exam, Vital Signs, ECOG PS, treatment administration, AEs, conmeds, hematology, serum chemistry visit days have +/- 7 day window for Cycles > 6. Assessments must be done prior to treatment administration. Assessments must be done within the specified window, but only prior to initiation of next cycle.
4 Serum virology to include HBsAg, HBsAb, HBc antibody, HCV antibody and CMV. If HBc antibody, HCV antibody or CMV is positive, subjects must be evaluated for the presence of active HBV, HCV or CMV by DNA (PCR).

⁵ Every 3 months CMV screening by PCR. CMV surveillance will discontinue 30 days after last dose of umbralisib, or as otherwise clinically indicated per investigator discretion.

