8.6 PARTIAL RESPONSE

To satisfy criteria for a PR, all of the following criteria must be met:

- No evidence of new disease
- A change in disease status meeting ≥2 of the following criteria, with 2 exceptions in which
 only 1 criterion is needed: 1) only lymphadenopathy is present at baseline; 2) only
 lymphadenopathy and lymphocytosis are present at baseline. In these 2 cases, only
 lymphadenopathy must improve to the extent specified below:
 - In a subject with baseline lymphocytosis (ALC ≥4 x 10⁹/L), a decrease in peripheral blood ALC by ≥50% from baseline or a decrease to <4 x 10⁹/L
 - A decrease by ≥50% from the baseline in the SPD of the target nodal lesions (if applicable)
 - In a subject with enlargement of the spleen at baseline, a splenomegaly response as defined in Section 8.3.2
 - In a subject with enlargement of the liver at baseline, a hepatomegaly response as defined in Section 8.3.2
 - A decrease by ≥50% from baseline in the CLL marrow infiltrate or in B-lymphoid nodules
- No target, splenic, liver, or non-target disease with worsening that meets the criteria for definitive PD
- Peripheral blood counts meeting 1 of the following criteria:
 - ANC >1.5 x 10⁹/L or >50% increase over baseline without need for exogenous growth factors (e.g., G-CSF)
 - Platelet count ≥100 x 10⁹/L or ≥50% increase over baseline without need for exogenous growth factors
 - Hemoglobin ≥110 g/L (11.0 g/dL) or ≥50% increase over baseline without red blood cell transfusions or need for exogenous growth factors (e.g., erythropoietin)

The proportion of subjects who achieve a PR with lymphocytosis will be recorded.⁷

TGR-1202-201-CLL

To satisfy criteria for SD, the following criteria must be met:

- No evidence of new disease
- There is neither sufficient evidence of tumor shrinkage to qualify for PR nor sufficient evidence of tumor growth to qualify for definitive PD

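### Target nodes may be peripheral only and need not be the largest, so section 8.6 can score a PR while an unmeasured deep mass grows short of PD, and Appendix A differs

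*Combined protocol and SAP*

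**What the plan says.** Section 8.3.1 sets the selection rule: "At baseline, up to 6 lymph nodes should be selected as target lesions", where measurable disease is present. Spread is advisory ("Ideally, the target lesions should be located in disparate regions of the body"). It then states that "Only peripheral nodes need be selected as target lesions", and adds of the deep sites that "it is optimal if mediastinal and retroperitoneal areas of disease are assessed whenever these sites are involved". Any node above 1.5 cm by 1.0 cm qualifies, and nothing ranks nodes by size.

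The schedule in section 5 lists CT of neck, chest, abdomen and pelvis at baseline and at each response evaluation. Section 8 allows MRI instead.

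Section 8.6 scores the nodal part of PR as "A decrease by ≥50% from the baseline in the SPD of the target nodal lesions (if applicable"). Where baseline disease is nodes only, or nodes plus lymphocytosis, this is the one disease-change criterion needed. The same section adds a bar on PR: "No target, splenic, liver, or non-target disease with worsening that meets the criteria for" definitive PD.

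Under 8.3.3, measurable nodes not chosen as targets may be treated as non-target lesions, up to six of them. They need no measurement and are followed only as present or absent.

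**The concern.** The scans already show the deep nodes, but the quantity that decides nodal PR need not include them. The investigator selects the targets and, under 9.7, also determines response and progression. The trial is single-arm, and 8.2 foresees confirmation of images only if the sponsor asks. If the targets are small superficial nodes and the bulk lies in the mediastinum or retroperitoneum, target SPD can move one way and the remaining nodal disease the other.

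ORR is at stake directly, and DOR with it, because a PR starts the DOR clock. With about 50 subjects analysed, each PR that turns on this point moves ORR by 1/50 = 2 percentage points.

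**Working it through.** The plan states no figure for how much nodal disease the targets must cover, so there is none to reproduce. The stated 82% power does not depend on this point.

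**Inputs from the documents**
- Nodal PR: target SPD down at least 50% from baseline (8.6).
- PD, any of these (8.8): target SPD up at least 50% from nadir; longest diameter (LD) of an individual node up at least 50% from nadir; unequivocal growth of non-target disease, with no number attached.
- At most six targets, each above 1.5 × 1.0 cm (8.3.1).

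**Assumed inputs** (the documents give no node sizes): six peripheral targets of 1.6 × 1.1 cm; one untargeted retroperitoneal mass of 8 × 6 cm. The target products halve, and both diameters of the mass grow 20%.

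**Illustration**
1. Target SPD: 6 × 1.6 × 1.1 = 10.56 cm², falling to 5.28 cm² (−50%). The nodal PR criterion is met.
2. Mass: 8 × 6 = 48 cm², rising to 9.6 × 7.2 = 69.12 cm² (area +44%, LD +20%). This is below the 50% LD rule.
3. Total: 10.56 + 48 = 58.56 cm², rising to 5.28 + 69.12 = 74.40 cm² (+27%).
4. With the mass as a target in place of one peripheral node: 5 × 1.76 + 48 = 56.80 cm², rising to 5 × 0.88 + 69.12 = 73.52 cm² (+29%). There is no nodal PR, but the rise is also below the 50% SPD rule for PD. The subject moves from PR to SD, and the progression date does not change.

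**General form.** Let T be target SPD and D untargeted SPD. If T falls by exactly half, total area rises once D grows by a fraction g > 0.5 × T/D. If growth is proportional, the matching LD growth is √(1+g) − 1.

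| D/T | area growth g | LD growth |
|---|---|---|
| 1 | 50% | 22% |
| 2 | 25% | 12% |
| 3 | 17% | 8% |
| 5 | 10% | 5% |

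All are well below the 50% LD rule.

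**What it takes to reach PFS.** Assume six targets of 2.0 × 1.5 cm shrinking to 1.4 × 1.0 cm (18.0 to 8.4 cm², −53%) and a mass growing from 8 × 6 to 11.5 × 8.5 cm (48 to 97.75 cm², LD +44%). The total goes from 66.0 to 106.15 cm² (+61%). With baseline as nadir, an SPD that included the mass would pass the 50% rule for PD, while target-only SPD and the LD rule would not. This needs growth from 8 to 11.5 cm that nobody calls unequivocal.

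**Rules side by side for the growing mass**
- 8.6: target SPD is satisfied. PR is barred only if the mass meets definitive PD.
- 8.8: the LD rule is not limited to targets, but it needs a nadir LD that 8.3.3 does not require for untargeted nodes. Unequivocal growth is left to judgement.
- 8.5: CR requires nodal non-target disease to return to normal, so the mass blocks CR.
- Appendix A: the nodal PR criterion fails if any node has increased, with tolerance only for increases under 25% in nodes below 2 cm. With nodes only, or nodes plus lymphocytosis, two Group A criteria then cannot be met and there is no PR.

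**The case against.** The best defence is that untargeted nodes are not ignored. They can be non-target lesions, their worsening to PD bars PR, and 8.8 counts both unequivocal non-target growth and a 50% LD rise in any node as PD. Sections 8 and 9.9.2.1 tie response to the 2008 iwCLL criteria, which Appendix A reproduces, and under them the illustrated mass defeats nodal PR. These safeguards are real and narrow the gap. They do not close it: unmeasured nodes followed as present or absent leave no required record against which either size rule can be checked, and 8.6 omits the Appendix A condition.

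A reader might infer that the rule inflates ORR. The documents do not support a direction. Targets are fixed at baseline, before treatment, without knowledge of which nodes will shrink, and nothing in the plan says that peripheral nodes respond better than deep ones. Small targets can also bring SPD progression forward: from a nadir of 5.28 cm², a rise of 2.64 cm² is enough.

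A reader might also infer that PFS is delayed. The main illustration does not show this (+27% or +29%, both under 50%), and the larger example depends on striking growth going uncalled.

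The illustration pairs near-minimum targets with a large omitted mass, against the advisory guidance in 8.3.1. It shows what is permitted, not what is likely. Nor does the nodal criterion stand alone in 8.6: no new disease, no definitive PD and a blood-count condition also apply.

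**Conclusion.** The concern holds in a limited form. Sections 8.3.1, 8.3.3 and 8.6 together permit a PR while an untargeted deep mass grows, so long as the growth is under 50% in LD and not judged unequivocal. Where untargeted disease is three times target SPD and target SPD has halved, about 8% proportional growth in LD is enough for total nodal area to rise. Sections 8.6 and Appendix A give different answers for the same subject and must be reconciled.

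The direct exposure is PR, hence ORR and DOR. CR is protected by 8.5. An effect on the primary endpoint is possible only through late or missed PD in unmeasured deep nodes, and its size is not established. All node sizes are assumptions. How often the situation arises, and which way it would shift ORR, cannot be known from the documents. This is a worthwhile, inexpensive improvement, and no sample-size or power figure changes.

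**What to change.** 1. In 8.3.1, replace the sentence that lets peripheral nodes suffice with: *Select as targets the largest measurable nodes (up to 6) on the baseline CT/MRI, from different regions, including the largest mediastinal and retroperitoneal nodes when involved.*
2. Reconcile 8.6 with Appendix A on whether growth of any node prevents a PR. If that condition is kept, say how it is to be checked for untargeted nodes, which 8.3.3 leaves unmeasured.
3. For subjects already enrolled, report the number with peripheral-only targets. Give ORR as planned, and again with PRs in those subjects counted as non-responses.

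The cost is a site instruction and one extra table: same scans, same six-node limit, no added reader. The limitation is reach. The selection rule works prospectively only. Enrollment was expected to take about 12 months and the current version is dated March 2019, after a first amendment in July 2016. Enrollment status is not stated, but if it is complete, items 2 and 3 carry the benefit. Section 9.7 asks that scans be kept on file, which should help identify the subjects concerned.

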8.3.2 SPLEEN AND LIVER

Both the spleen and liver will be assessed by CT/MRI scan and/or by physical examination at baseline and as per the study assessment schedule. The baseline and nadir values for the longest vertical dimension (LVD) of each organ will be used as reference to further characterize the objective tumor response of the measurable dimensions of the CLL during treatment. All spleen and liver LVD measurements should be recorded in centimeters.

By imaging, the spleen will be considered enlarged if it is >12 cm in LVD, with the LVD being obtained by multiplying the number of sections on which the spleen is visualized by the thickness of the

sections (e.g., if the spleen is seen in 14 contiguous cross-sectional images with 0.5-cm thickness, the LVD is recorded as 7 cm).

For subjects with splenomegaly at baseline or at the splenic LVD nadir, respective response and progression evaluations of the spleen will consider only changes relative to the enlargement of the spleen at baseline or nadir, not changes relative to the total splenic LVD.

A 50% decrease (minimum 2 cm decrease) from baseline in the enlargement of the spleen in its LVD or decrease to ≤ 12 cm by imaging is required for declaration of a splenomegaly response. Conversely, an increase in splenic enlargement by $\geq 50\%$ from nadir (minimum increase of 2 cm) is required for declaration of splenic progression. By imaging, the liver will be considered enlarged if it is >18 cm in LVD.

A 50% decrease (minimum 2 cm decrease) from baseline in the enlargement of the liver in its LVD or decrease to \leq 18 cm is required for declaration of a hepatomegaly response. Conversely, an increase in liver enlargement by \geq 50% from nadir (minimum increase of 2 cm) is required for declaration of hepatic progression.

